#### **7.7.8 Unscheduled Visit**

An unscheduled visit is allowed at any time if in the investigator's opinion it is warranted. The following procedures may be performed at the Unscheduled Visit if required.

- LFGS assessments
- POL assessments
- pGAI assessment
- iGAI assessment
- Lip function evaluation
- Lip sensation evaluation

- Lip texture evaluation
- Lip firmness evaluation
- Lip symmetry evaluation
- Lip movement/function evaluation
- Vision Evaluation (Snellen visual acuity, confrontational visual fields, ocular motility)
- Assess AEs
- Swelling Assessment
- Subject Satisfaction with lips (VAS)
- Assess concomitant medications/treatments
- Complete CRFs

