### **8.4 Safety Analyses**

Adverse events will be coded to system organ class and preferred terms using the Medical Dictionary for Regulatory Activities (MedDRA, Version 20 or higher).

Frequency and percentage of subjects reporting treatment-emergent adverse events (TEAEs) will be tabulated for each treatment by preferred terms and further by severity and relationship to study device. In summaries of severity and relationship, subjects reporting more than one event in a treatment arm that are mapped to the same preferred term will be counted only once in that treatment arm under the strongest severity and relationship, respectively. In addition, visual related TEAEs will be summarized separately for each treatment by preferred term.

Assessment results of lip function, lip sensitivity, lip texture, lip firmness, lip symmetry, and lip movement/function will be summarized with frequency and percentage for each scheduled visit.

Safety analyses will be conducted using the ITT population.

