5.1 Methodological Considerations

SAS software (version 9.4 or higher) will be used for all data analyses and tabulations.

Two-sided hypothesis testing will be conducted for all inferential analyses. Resulting p-values less than 0.05 will be considered statistically significant. To control the overall error rate, a hierarchical approach will be applied. Upon the significance of the primary efficacy outcome, secondary endpoints will be analyzed and no adjustment to the p-values will be applied to multiple comparisons. For this non-inferiority study, the null hypothesis to be tested for all the secondary endpoints is that there is no difference between the two products, and all statistical comparisons for these endpoints will be considered descriptive (non-inferential).

No interim analyses are planned.

All the data points will be presented in subject data listings.

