5.6.3 Other Variables

Investigator Ease of Use Assessment

Overall ease of use of the device will be evaluated by the Treating Investigator using the numerical rating scale (NRS) from 0 being not easy to 10 being most easy at Visit 1/Day 1 and for subjects who have touch-up treatment at Visit 2/Month 1. It will be summarized for the AT subjects descriptively with mean, SD, minimum, median, and maximum.

Lip Evaluations

Lip function, lip sensation, lip texture, lip firmness, lip symmetry, and lip movement/function will be evaluated by the Blinded Evaluating Investigator at each visit. These variables will be summarized using frequency and percent of subjects by categories of incidence.

Concomitant Medications

Concomitant medications will be coded using the World Health Organization (WHO) Drug Dictionary, Version March 2013 or later, and will be presented in data listings.

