O:\Studies\Prolenium\SYM 2018-02\Biometrics\Programs\Tables\vxix.sas ran on Month Day, Year at hh:mm on data from Month, Day, Year.

Note:

Table 14.2.3.1 will be used as the shell for the following table:

Table 14.2.3.2 – Other Efficacy: Investigator Global Aesthetic Improvement (iGAI) by Visit Based on Observed Data

Table 14.2.3.3 – Other Efficacy: Swelling Assessment by Visit Based on Observed Data

Study Visit	Category	Modified Intent-to-Treat		Per-Protocol	
		PN40082	Restylane Silk	PN40082	Restylane Silk
Visit 2/Month 1	N	0	0	0	0
	0 = None	0 (0%)	0 (0%)	0 (0%)	0 (0%)
	1 = Minimal	0 (0%)	0 (0%)	0 (0%)	0 (0%)
	2 = Mild	0 (0%)	0 (0%)	0 (0%)	0 (0%)
	3 = Moderate	0 (0%)	0 (0%)	0 (0%)	0 (0%)
	4 = Severe	0 (0%)	0 (0%)	0 (0%)	0 (0%)
Visit 3/Month 2					
...					
Visit 5/Month 6	N	0	0	0	0
	0 = None	0 (0%)	0 (0%)	0 (0%)	0 (0%)
	1 = Minimal	0 (0%)	0 (0%)	0 (0%)	0 (0%)
	2 = Mild	0 (0%)	0 (0%)	0 (0%)	0 (0%)
	3 = Moderate	0 (0%)	0 (0%)	0 (0%)	0 (0%)
	4 = Severe	0 (0%)	0 (0%)	0 (0%)	0 (0%)

Source: Listing 16.2.6.1.3

O:\Studies\Prolenium\SYM 2018-02\Biometrics\Programs\Tables\cxxx.sas ran on Month Day, Year at hh:mm on data from Month, Day, Year.

Table 14.2.3.4 – Other Efficacy: Percent of Subjects with Treatment Success on Lip Fullness Grading Scale (LFGS) at Visit 3/Month 2 for Upper Lips and Lower Lips Based on Observed Data

Population	Category	Upper Lips		Lower Lips	
		PN40082	Restylane Silk	PN40082	Restylane Silk
Per-Protocol	N	0	0	0	0
	n (%) of Treatment Success	0 (0.0%)	0 (0.0%)	0 (0.0%)	0 (0.0%)
Modified Intent-to-Treat	N	0	0	0	0
	n (%) of Treatment Success	0 (0.0%)	0 (0.0%)	0 (0.0%)	0 (0.0%)

Treatment success is defined as an achievement of at least a 1-grade increase from baseline on the overall LFGS, where LFGS: 0=Very Thin Lips, 1=Thin Lips, 2=Moderately Thick Lips, 3=Thick Lips, 4=Full Lips.

Source: Listing 16.2.6.2.2, 16.2.6.2.3

O:\Studies\Prolenium\SYM 2018-02\Biometrics\Programs\Tables\xxx.sas ran on Month Day, Year at hh:mm on data from Month, Day, Year.

Note:

Table 14.2.3.4 will be used as the shell for the following table:

Table 14.2.3.5 – Other Efficacy: Percent of Responders on Perioral Lines at Rest (POL) Severity Scale at Visit 4/Month 3 for Upper Lips and Lower Lips Based on Observed Data

With first footnote changed to the following:

Responder is defined as a subject demonstrating at least 1-point improvement, i.e., decrease in severity, from baseline POL severity, where POL severity: 0=None, 1=Mild, 2=Moderate, 3=Severe.

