	n (%) subjects able to sip liquid through a straw	0 (0%)	0 (0%)
Visit 5/Month 6	N	0	0
	n (%) subjects able to sip liquid through a straw	0 (0%)	0 (0%)

Source: Listing 16.2.4.8

O:\Studies\Prollenium\SYM 2018-02\Biometrics\Programs\Tables\ccx.sas ran on Month Day, Year at hh:mm on data from Month, Day, Year.

Note:

Table 14.3.4.1 will be used as the shell for the following table:

Table 14.3.4.2 – Lip Sensation Test (Cotton Wisp) by Visit for As-Treated Population

Table 14.3.4.3 – Lip Sensation Test (0.4G Monofilament) by Visit for As-Treated Population

Table 14.3.4.4 – Lip Texture Evaluation by Visit for As-Treated Population

Study Visit	Category	PN40082	Restylane Silk
Visit 1/Day 1 (Prior to injection)	N	0	0
	n (%) Normal	0 (0%)	0 (0%)
	n (%) Abnormal	0 (0%)	0 (0%)
	- n (%) Abnormal: Mild	0 (0%)	0 (0%)
	- n (%) Abnormal: Moderate	0 (0%)	0 (0%)
	- n (%) Abnormal: Severe	0 (0%)	0 (0%)
Visit 2/Month 1 (Prior to touch-up)	...		
	...		
Visit 3/Month 2			
Visit 4/Month 3			
Visit 5/Month 6			

Source: Listing 16.2.4.9

O:\Studies\Prollenium\SYM 2018-02\Biometrics\Programs\Tables\ccx.sas ran on Month Day, Year at hh:mm on data from Month, Day, Year.

Note:

Table 14.3.4.4 will be used as the shell for the following table:

Table 14.3.4.5 – Lip Firmness Evaluation by Visit for As-Treated Population

Table 14.3.4.6 – Lip Symmetry Evaluation by Visit for As-Treated Population

Table 14.3.4.7 – Lip Movement/Function Evaluation by Visit for As-Treated Population

Study Visit	Category	PN40082	Restylane Silk
Visit 1/Day 1 (Prior to injection)	N	0	0
	n (%) Normal – Subject’s ability to pucker lips	0 (0%)	0 (0%)
	n (%) Normal – Subject’s ability to blow with lips	0 (0%)	0 (0%)
	n (%) Normal – Subject’s ability to pronounce words that begin with “W”	0 (0%)	0 (0%)
Visit 2/Month 1 (Prior to touch-up)	...		
	...		
Visit 3/Month 2			
Visit 4/Month 3			
Visit 5/Month 6			

Source: Listing 16.2.4.8

O:\Studies\Prolenium\SYM 2018-02\Biometrics\Programs\Tables\ccx.sas ran on Month Day, Year at hh:mm on data from Month, Day, Year.

Table 14.3.5 – Other Analysis: Assessment of Blinding to Subjects and Evaluators at End of Study

Assessed by Subject or Evaluator	Treatment Subject Received	Treatment Guessed	n/N ¹ (%)	P-value and 90% Confidence Interval ²
By Subject	PN40082	PN40082	0/0 (0%)	(0.0%, 0.0%)
		Restylane Silk	0/0 (0%)	
		Unsure	0/0 (0%)	
	Restylane Silk	PN40082	0/0 (0%)	
		Restylane Silk	0/0 (0%)	
		Unsure	0/0 (0%)	
Overall Correct Guesses		0/0 (0%)		

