Site-Subject	Analyses	Sitting Systolic BP (mmHg)	Sitting Diastolic BP (mmHg)	Heart Rate (bpm)	Oral Temperature (°F)	Respiratory Rate (breath/min)	Urine Pregnancy Test	
							Test Results	Test Date
Treatment:								

Analyses: A = As-Treated (AT) Analyses only, M = Modified Intent-to-Treat (MITT) Analyses, P = Per-Protocol Analyses

O:\Studies\ Prolenium\SYM 2018-02\Biometrics\Programs\Listing\xxx.sas ran on Month Day Year at hh:mm on data from Month Day, Year.

Listing 16.2.4.7 – Vision Evaluation

Site- Subject	Analyses	Study Visit (Time Point)	Confrontational Visual Field Results (Specify if abnormal)	Ocular Visual Field Results (Specify if abnormal)	Subject wearing corrective lenses?	Snellen Visual Acuity Score		Vision at Post-Baseline Visit	
						Left Eye	Right Eye	Initials of Assessor	Changed significantly from baseline?
Treatment:									

Analyses: A = As-Treated (AT) Analyses, M = Modified Intent-to-Treat (MITT) Analyses, P = Per-Protocol Analyses

O:\Studies\ Prolenium\SYM 2018-02\Biometrics\Programs\Listing\xxx.sas ran on Month Day Year at hh mm on data from Month Day, Year.

Listing 16.2.4.8 – Lip Function, Lip Sensation and Lip Movement/Function Tests

Site- Subject	Analyses	Study Visit (Time Point)	Able to sip liquid through a straw?	Assessor of Lip Function	Able to feel sensation of a cotton wisp?	Able to feel sensation of a 0.4G monofilament	Assessor of Lip Sensation	Ability to pucker lips	Ability to blow with lips	Ability to pronounce words that begin with “W”	Assessor of Lip Movement /Function
------------------	----------	-----------------------------	--	--------------------------------	---	--	---------------------------------	------------------------------	---------------------------------	---	---

Treatment:

Analyses: A = As-Treated (AT) Analyses, M = Modified Intent-to-Treat (MITT) Analyses, P = Per-Protocol Analyses

O:\Studies\Prolenium\SYM 2018-02\Biometrics\Programs\Listing\xxx.sas ran on Month Day Year at hh mm on data from Month Day, Year.

Listing 16.2.4.9 – Lip Texture, Lip Firmness and Lip Symmetry Evaluations

Site-Subject	Analyses	Study Visit (Time Point)	Lip Texture		Lip Firmness		Lip Symmetry	
			Normal or Abnormal (severity)	Evaluator	Normal or Abnormal (severity)	Evaluator	Normal or Abnormal (severity)	Evaluator
Treatment:								

Analyses: A = As-Treated (AT) Analyses, M = Modified Intent-to-Treat (MITT) Analyses, P = Per-Protocol Analyses

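### SAP Tables 14.3.4.1 to 14.3.4.7 summarize the lip safety evaluations at scheduled visits only, so a finding graded only at an unscheduled visit enters no between-arm lip summary

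*SAP*

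**What the plan says.** Protocol 8.4 plans the lip function, sensation, texture, firmness, symmetry and movement results as counts and percentages that "will be summarized with frequency and percentage for each scheduled visit". SAP 5.6 places these evaluations among the key safety variables. SAP 5.6.3 adds only that "These variables will be summarized using frequency and percent of subjects by categories of incidence" and does not mention unscheduled visits.

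The shells of Tables 14.3.4.1 to 14.3.4.7, such as "Table 14.3.4.4 – Lip Texture Evaluation by Visit for As-Treated Population", have rows for Visits 1 to 5. Visit 1 is before injection, so four rows are post-treatment. None of the seven tables has a row for unscheduled visits, for any post-injection visit, or for the worst result.

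Protocol 7.7.8 states that "An unscheduled visit is allowed at any time" if the investigator thinks it warranted, and that "The following procedures may be performed at the Unscheduled Visit if required". All six lip evaluations are on the list that follows.

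SAP 5.1 promises that "All the data points will be presented in subject data listings". Listing 16.2.4.9 ("Lip Texture, Lip Firmness and Lip Symmetry Evaluations") and Listing 16.2.4.8 have a visit/time-point column that can hold unscheduled results, and Listing 16.2.1.3 gives the number and study days of unscheduled visits.

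**The concern.** Scheduled lip examinations after injection are sparse. The Day 3 and Day 14 contacts are telephone calls, so the first scheduled examination is at Day 28 ± 2. Day 112 and Day 140 are also calls, which leaves nominally 84 days (Day 84 to Day 168) without one. A lip finding that comes and goes between these dates receives a texture, firmness, symmetry, function, sensation or movement grade only if the subject is examined at an unscheduled visit. The tables then leave that grade out.

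For AEs, SAP 5.6.1 counts each subject once per preferred term at the strongest severity. The lip measures have no equivalent. A reader who wants to know how many subjects in each arm ever had a new lip abnormality would have to build the answer from the listings after unblinding. A row specified in advance avoids that post hoc choice.

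**Working it through.** **Step 1: is there a stated rate to reproduce?** No. Neither document gives a lip abnormality rate or an unscheduled-visit rate. The only usable figure is the arm size. Protocol 8.5 gives 126 per-protocol subjects at an 80% share: 126/0.80 = 157.5, rounded up to 158, or 79 per arm. This reproduces, and it serves below only as an assumed denominator.

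**Step 2: where does an unscheduled lip result go?**

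| Output | Includes unscheduled lip results? | Compares arms? |
|---|---|---|
| Tables 14.3.4.1 to 14.3.4.7 | No (Visits 1 to 5 only) | Yes |
| Listings 16.2.4.8 and 16.2.4.9 | Yes | No |
| TEAE tables (SAP 5.6.1) | Only if recorded as an AE | Yes, on the AE severity scale |

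The third line recovers part of the information. Protocol 7.9.6.1 grades AE severity by tolerability and interference with daily activity. Protocol Tables 2 to 4 grade physical findings: visible irregularity, resistance to pressure, millimetres of asymmetry. One scale does not give the other. No passage requires an abnormal lip evaluation to be recorded as an AE.

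**Step 3: what would each omitted subject be worth?** With N assessed subjects in an arm, each subject abnormal only at an unscheduled visit adds 100/N percentage points to a whole-study figure.

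- N = 79 (assumption: all randomized subjects assessed): 1 subject = 1.27 points; 2 = 2.5; 4 = 5.1; 8 = 10.1; none = 0.
- N = 63 (the per-protocol target, as a low case): 100/63 = 1.59 points per subject.

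The percentages at Visits 1 to 5 do not change in any of these cases.

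**Step 4: how much can a scheduled-visit summary miss?** This is an illustration only. Assume onset uniform over Days 1 to 168 (a span of 167 days) and visits exactly on Days 28, 56, 84 and 168. A finding of duration D is present at a visit on day v if onset lies between v − D and v. The share seen is the length of the union of these intervals, divided by 167.

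- D = 7: 4 × 7/167 = 16.8%.
- D = 18: 4 × 18/167 = 43.1%.
- D = 49: Days 1 to 84 (83) plus Days 119 to 168 (49) = 132/167 = 79.0%.

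The comparator label attached to the protocol suggests where real durations may lie. It says that most delayed-onset injection site reactions resolved within 18 days. For lip disorder after first treatment, it gives a mean duration of 49.1 days (median 38.5). A finding that starts on Day 1 must last 28 − 1 = 27 days to be seen at Visit 2 on its nominal day.

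Short findings can thus fall between visits, while the longer-lasting ones would mostly be seen. How many of the missed ones would be graded at an unscheduled visit is unknown.

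**The case against.** The strongest reply is that nothing is wrong with the tables. They report status at each visit, as Protocol 8.4 prespecifies, and unscheduled data would not alter any of their figures. This stands. A reader might infer that on-study lip abnormality rates are understated. The documents do not support that: they define no cumulative rate, and the by-visit figures mislead only if they are read as cumulative and only if unscheduled-only abnormalities occur.

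A second tempting reading is that reactions between visits can be graded only at unscheduled visits. That is also wrong. AEs are collected at every visit and call, including Days 112 and 140, and diaries cover two weeks after each treatment. AEs carry severity grades, and the TEAE tables are not limited by visit. Many short reactions will be compared between arms there. What those tables do not carry is the lip grade itself.

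Third, unscheduled visits need not be problem-driven. Protocol 7.7.8 leaves them to the investigator's judgement and makes the lip evaluations optional. A return prompted by symptoms is likely, since Protocol 7.4.3 tells subjects to contact the site about substantial swelling, but it remains an inference. Such visits also make a whole-study row depend partly on how often subjects come back. That calls for a footnote; it is not a reason to leave the row out.

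Fourth, a crude worst-result row would be flawed. Abnormal texture, abnormal firmness and mild asymmetry are not exclusion criteria, so pre-existing findings would count as post-injection ones. Dividing by the whole arm would also treat unexamined subjects as normal. Both objections are sound, and the row proposed below is defined to meet them.

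Finally, the label reports little abnormality on these measures: nothing remarkable in the pivotal study, and two mild, resolved texture findings among 60 subjects in the cannula study. The yield may be small.

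**Conclusion.** The gap is real but minor. Lip grades obtained only at unscheduled visits are listed, and may be counted as AEs, but they enter no between-arm lip summary, and no whole-study lip summary exists. The size of the omission cannot be computed. It is 1.27 percentage points per affected subject if 79 per arm are assessed, and zero if no such subjects arise. No contrast between the arms can be inferred from the documents.

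A reader might extend the point to "Table 14.2.3.3 – Other Efficacy: Swelling Assessment by Visit Based on Observed Data". It does not belong there: that is an efficacy table on the mITT and per-protocol populations, and its endpoint is defined at scheduled visits in Protocol 7.8.3 and SAP 5.5.3.

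The conclusion rests on the shells as drafted. SAP section 6 calls them examples that can be changed during analysis, so the row could be added in any case. The case for adding it now is that its definition would be fixed before results are seen.

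**What to change.** Keep all by-visit rows. Add to each of Tables 14.3.4.1 to 14.3.4.7 one row per arm: *new or worsened from baseline at any post-injection assessment, scheduled or unscheduled (worst result)*.

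- Count each As-Treated subject once.
- For the graded measures (texture, firmness, symmetry), show the worst grade among subjects whose grade exceeds baseline. For the two-level measures (function, sensation, movement), count a change from normal to abnormal.
- Use as denominator the subjects with at least one post-injection assessment of that measure.
- Footnote that unscheduled examinations are optional and may be symptom-driven, so the row shows detected abnormalities.

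Align the wording of Protocol 8.4 or SAP 5.6.3 so that the text names this summary alongside the by-visit one. Leave the swelling table unchanged.

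The cost is seven added rows per arm from data already collected and listed. No visit, procedure, endpoint or sample size changes. The one drawback is the uneven ascertainment that the footnote states.
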